7.4.5.7. Decline in Renal Function

Participants who experience an increase in serum creatinine from Baseline of 45 micromoles/liter ($\mu\text{Mol/L}$) (or 0.5 milligrams/deciliter [mg/dL]) should return for a confirmatory assessment within 2 to 4 weeks. A urinalysis and urine albumin/creatinine and urine total protein/albumin ratios should also be done at this confirmatory visit. If the creatinine increase is confirmed, the investigator should contact the study medical monitor to discuss additional follow-up and medical management.

Participants who have a decline in the estimated GFR (using the CKD-EPI method) of $>50\%$ from Baseline must return for a confirmatory assessment as soon as possible [Levey, 2009]. A urinalysis and urine albumin/creatinine and urine protein/creatinine

ratios should also be done at this confirmatory visit. If the estimated GFR has declined by >50% (confirmed), then study drug should be withheld and the investigator should contact the study medical monitor to discuss the rationale for restarting study drugs (if appropriate). Consideration for confounding factors (e.g., background therapy, other medications, dehydration, concurrent conditions) should be taken into account, and a nephrology consult may be obtained.

7.4.5.7.1. Proximal Renal Tubule Dysfunctions (PRTD)

PRTD is defined as:

Confirmed rise in serum creatinine of ≥ 0.5 mg/dL from Baseline AND serum phosphate <2.0 mg/dL;

Either of the above accompanied by any two of the following:

Glycosuria (≥ 250 mg/dL) in a non-diabetic;

Low serum potassium (<3 mEq/L);

Low serum bicarbonate (<19 mEq/L).

Participants meeting criteria for PRTD must return for a confirmatory assessment within 2 weeks of diagnosis. A urinalysis should also be performed at the time of the confirmatory assessment. If PRTD is confirmed participants should have study drug withheld and the investigator should contact the Study medical monitor to discuss the rationale for restarting study drugs (if appropriate). Consideration for confounding factors (e.g., NRTI backbone, other medications, dehydration, concurrent conditions) should be taken into account, and a nephrology consult may be obtained. If study drug is reinitiated, it should have been withheld for no more than 4 weeks.

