- Participants who are not eligible to continue into the Maintenance Phase.
- Participants who are not eligible, or do not wish to continue on to the Extension Phase.
- Virologic withdrawal criteria as specified in Section 5.5.4 are met;
- Participant requires substitution of ART;
- Participant requires substitution or dose reduction of CAB LA or RPV LA (oral bridging supply and potential for a second loading dose may be permissible following discussion with the Medical Monitor).
- Liver toxicity where stopping criteria are met and no compelling alternate cause is identified (see Section 5.5.1);
- Renal toxicity are met and no compelling alternate cause is identified;
- QT interval (QTc) interval >550 msec from three or more tracings separated by at least 5 minutes and considered causally related to IP.
- Grade 4 clinical AE considered causally related to study drug;
- Participant has a Grade 3 or higher rash or Grade 2 rash with evidence of systemic involvement and no compelling alternative cause is identified
- Pregnancy (intrauterine), regardless of termination status of pregnancy.
- Participant withdrew consent

Efficacy data for participants withdrawing from the study will be considered evaluable up to the point at which they are withdrawn using the same criteria for evaluability as for participants who complete the study.

Safety data for all participants who receive any amount of study drug, including participants who withdraw from the study, will be included in evaluations of safety.

All data from the Withdrawal visit will be recorded, as they comprise an essential evaluation that should be done prior to discharging any participant from the study.

The following actions must be taken in relation to a participant who fails to attend the clinic for a required study visit:

- a. The site must attempt to contact the participant and re-schedule the missed visit as soon as possible.

- b. The site must counsel the participant on the importance of maintaining the assigned visit schedule and ascertain whether or not the participant wishes to and/or should continue in the study.

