7.4.4.4. Grade 4 Toxicity/Adverse Event

- Participants who develop a Grade 4 AE or toxicity must have IP permanently discontinued. However, if the Investigator has compelling evidence that the AE is not causally related to the IP, dosing may continue after discussion with, and assent from, the Medical Monitor. Participants should be rechecked each week until the AE returns to Grade 2.
- Participants experiencing Grade 4 AEs requiring permanent discontinuation of IP should be followed weekly until resolution of the AE and encouraged to complete the withdrawal and follow-up study evaluations as noted above. Any participant receiving at least one dose of CAB LA and /or RPV LA who discontinue IP / Withdraw will initiate treatment with HAART and enter the LTFU Phase for 52 weeks of follow up.
- Participants with Grade 4 asymptomatic laboratory abnormalities should be investigated for all potential non-drug related causes, and, following discussion with the Medical Monitor, may continue therapy if the Investigator has compelling evidence that the toxicity is not related to IP, with the exception of liver chemistry stopping criteria (See Section 7.4.5.1). An in-clinic follow-up visit will be performed approximately 4 weeks after the last dose of study medication if AEs, SAEs, or laboratory abnormalities considered potentially harmful to the participant are ongoing at the last on-study visit. Isolated Grade 4 lipid abnormalities do not require withdrawal of IP.

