< 7 days of age	11.5 to < 12.4 2.88 to < 3.10	12.4 to < 12.9 3.10 to < 3.23	12.9 to < 13.5 3.23 to < 3.38	≥ 13.5 ≥ 3.38
Calcium (Ionized), High (mg/dL; mmol/L)	> ULN to < 6.0 > ULN to < 1.5	6.0 to < 6.4 1.5 to < 1.6	6.4 to < 7.2 1.6 to < 1.8	≥ 7.2 ≥ 1.8
Calcium, Low (mg/dL; mmol/L) ≥ 7 days of age	7.8 to < 8.4 1.95 to < 2.10	7.0 to < 7.8 1.75 to < 1.95	6.1 to < 7.0 1.53 to < 1.75	< 6.1 < 1.53
< 7 days of age	6.5 to < 7.5 1.63 to < 1.88	6.0 to < 6.5 1.50 to < 1.63	5.50 to < 6.0 1.38 to < 1.50	< 5.50 < 1.38
Calcium (Ionized), Low (mg/dL; mmol/L)	< LLN to 4.0 < LLN to 1.0	3.6 to < 4.0 0.9 to < 1.0	3.2 to < 3.6 0.8 to < 0.9	< 3.2 < 0.8
Cardiac Troponin I, High	NA	NA	NA	Levels consistent with myocardial infarction or unstable angina as defined by the local laboratory
Creatine Kinase, High	3 to < 6 x ULN	6 to < 10x ULN	10 to < 20 x ULN	≥ 20 x ULN
Creatinine, High *Report only one	1.1 to 1.3 x ULN	> 1.3 to 1.8 x ULN OR Increase to 1.3 to < 1.5 x participant's baseline	> 1.8 to < 3.5 x ULN OR Increase to 1.5 to < 2.0 x participant's baseline	≥ 3.5 x ULN OR Increase of ≥ 2.0 x participant's baseline
Creatinine Clearance¹⁴ or eGFR, Low *Report only one	NA	< 90 to 60 ml/min or ml/min/1.73 m ² OR 10 to < 30% decrease from participant's baseline	< 60 to 30 ml/min or ml/min/1.73 m ² OR 30 to < 50% decrease from participant's baseline	< 30 ml/min or ml/min/1.73 m ² OR ≥ 50% decrease from participant's baseline or dialysis needed
Glucose (mg/dL; mmol/L) Fasting, High	110 to 125 6.11 to < 6.95	> 125 to 250 6.95 to < 13.89	> 250 to 500 13.89 to < 27.75	≥ 500 ≥ 27.75
Nonfasting, High	116 to 160 6.44 to < 8.89	> 160 to 250 8.89 to < 13.89	> 250 to 500 13.89 to < 27.75	≥ 500 ≥ 27.75

¹⁴ Use the applicable formula (i.e., Cockcroft-Gault in mL/min or Schwartz, MDRD, CKD-Epi in mL/min/1.73m²). Sites should choose the method defined in their study and when not specified, use the method most relevant to the study population.

*Reminder: Choose the method that selects for the higher grade.

Chemistries

PARAMETER	GRADE 1 MILD	GRADE 2 MODERATE	GRADE 3 SEVERE	GRADE 4 POTENTIALLY LIFE- THREATENING
Glucose, Low (mg/dL; mmol/L) ≥ 1 month of age	55 to 64 3.05 to <3.55	40 to <55 2.22 to < 3.05	30 to <40 1.67 to < 2.22	<30 < 1.67
< 1 month of age	50 to 54 2.78 to < 3.00	40 to <50 2.22 to < 2.78	30 to <40 1.67 to < 2.22	<30 < 1.67

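### The renal safety rules are inconsistent as written: the proximal tubule definition has no single reading, a mandatory renal stop has no criterion, and a confirmed eGFR fall above 50% meets two different default instructions

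*Protocol*

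**What the plan says.** Five places in the protocol bear on renal findings.

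- **Section 7.4.5.7.1 (PRTD).** The two lead criteria are a confirmed creatinine rise of at least 0.5 mg/dL "from Baseline AND serum phosphate <2.0 mg/dL". The next line reads "Either of the above accompanied by any two of the following", and lists glycosuria in a non-diabetic, low serum potassium and low serum bicarbonate. On the consequence: "If PRTD is confirmed participants should have study drug withheld and the investigator should contact the Study medical monitor to discuss the rationale for restarting".
- **Section 5.5 (Withdrawal/Stopping Criteria).** Among the reasons for which treatment must be discontinued stands "Renal toxicity are met and no compelling alternate cause is identified".
- **Section 7.4.5.7 (Decline in Renal Function).** If an eGFR fall of more than 50% from baseline is confirmed, "then study drug should be withheld and the investigator should contact the study medical monitor to discuss the rationale for restarting study drugs". Restart is qualified by the words (if appropriate), and confounding factors are to be considered.
- **Section 7.4.4.4 (Grade 4).** "Participants who develop a Grade 4 AE or toxicity must have IP permanently discontinued". Dosing may continue if the investigator has compelling evidence that the event is not caused by study drug and the medical monitor assents. A later bullet sets the same evidential condition for asymptomatic Grade 4 laboratory abnormalities.
- **Appendix 2 (DAIDS table, creatinine clearance or eGFR, low).** The Grade 4 cell includes a fall of at least 50% from the participant's "baseline or dialysis needed".

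**The concern.** Withholding and stopping rules protect participants only if one laboratory result leads every site to the same action. Three things stand in the way here.

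1. The PRTD definition joins its lead criteria in one line and separates them in the next, so who qualifies depends on the reader.
2. Section 5.5 orders discontinuation for renal toxicity without saying what result triggers it.
3. The same confirmed eGFR result falls under a general rule whose default is a permanent stop and a specific rule whose default is a hold with restart open to discussion.

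The stake is higher than with a daily tablet. An injection cannot be withdrawn, and Section 6.9.1 says that plasma concentrations may be measurable for more than a year afterwards.

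**Working it through.** The plan gives no figure on this point to reproduce, and no event rates. The check is logical.

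**1. PRTD.** Let C be the creatinine rise, P the low phosphate, and S the number of the three supporting findings present. Five yes/no criteria give 2^5 = 32 patterns. Of the 8 patterns of the supporting findings, 3 + 1 = 4 have S ≥ 2 and 4 have S < 2.

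| Reading | Rule | Qualifying patterns |
|---|---|---|
| One rule, both leads needed | C and P and S ≥ 2 | 1 × 4 = 4 |
| One rule, either lead enough | (C or P) and S ≥ 2 | 3 × 4 = 12 |
| Two routes | (C and P), or (C or P) with S ≥ 2 | 8 + 2 × 4 = 16 |

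Two groups are in dispute:

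- Exactly one lead with S ≥ 2: 2 × 4 = 8 patterns. They are excluded by the first reading and included by the other two. An example is a confirmed creatinine rise with normal phosphate, glycosuria and low bicarbonate.
- Both leads with S < 2: 4 patterns. They are included only by the two-route reading.

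Together 8 + 4 = 12, which is the gap 16 − 4. These are counts of logical patterns, not expected frequencies.

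**2. Section 5.5.** The liver item in the same list names stopping criteria and cites Section 5.5.1. The QTc item gives a threshold. The renal item has neither a threshold nor a section number, and its sentence lacks a subject. No section sets out renal stopping criteria: Sections 7.4.5.7 and 7.4.5.7.1 both describe a hold followed by discussion of restart.

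**3. Confirmed eGFR fall above 50%.** Every fall above 50% is also a fall of at least 50%, so it is Grade 4 by Appendix 2. The grade reaches sites in practice: Section 7.4.2 has the central laboratory estimate GFR by CKD-EPI and grade results automatically on the DAIDS scale. The two rules then compare as follows.

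| Situation | Section 7.4.4.4 | Section 7.4.5.7 |
|---|---|---|
| No compelling evidence of another cause | Permanent discontinuation | Withhold; restart open to discussion |
| Compelling evidence of no causal relation | Dosing may continue after discussion | Withhold; restart open to discussion |

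They differ in both rows. Section 7.4.4.4 treats liver chemistry and isolated lipid abnormalities separately but names no renal exception, so nothing says that Section 7.4.5.7 takes precedence. The Grade 4 item in Section 5.5 does not settle it: it covers only clinical events judged related to study drug, which is narrower than Section 7.4.4.4.

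**The case against.** The strongest reply is that the rules form a sequence: hold, look for another cause, then restart or stop. The liver rules (Sections 5.5.1.1 and 5.5.1.3) and QTc rules (Sections 5.5.2 and 7.4.5.9) follow that pattern. Section 7.4.5.7 does not allow free restart either, since it asks for discussion, appropriateness and attention to confounders. Section 6.9 requires all decisions on interruption and resumption to be discussed with the medical monitor in advance. The example participant under PRTD would already be referred to the medical monitor by the creatinine rule in Section 7.4.5.7. The list layout in 7.4.5.7.1 may also have been clearer before text extraction.

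Much of this stands, and it makes a site acting alone on a wrong reading less likely. It does not remove the inconsistency. The protocol never states the sequence for renal events, the evidence needed for restart differs between the two sections, and the medical monitor works from the same text. Whatever the layout, the words of the PRTD definition contain no connector between its two parts.

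Two stronger readings are tempting and are not supported.

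- **That a confirmed fall above 50% is an unconditional mandatory stop.** Section 5.5 names no eGFR threshold and applies only when no convincing other cause is found. The permanent stop follows only through the DAIDS grade, and Section 7.4.4.4 lifts it on compelling evidence of no causal relation. It is a default.
- **That inconsistent stops would disturb the efficacy comparison.** One participant is 1/510, about 0.2 percentage points of an arm, against a 10-point margin and stated power of at least 99% for the key secondary endpoint. In the primary endpoint, the rule in Section 9.3.1 that counts discontinuations with HIV-1 RNA of 50 c/mL or more is for reasons other than adverse events. Both arms work under the same text, and the documents suggest no mechanism for a difference between them.

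**Conclusion.** The renal rules are wrong as written, in three limited ways: a PRTD definition that admits 4, 12 or 16 of 32 patterns, a mandatory-discontinuation item without a criterion, and two different default instructions for a confirmed eGFR fall above 50%. The first two are visible in the text alone. The third rests on applying Appendix 2 grading to the eGFR result, as Section 7.4.2 directs. How many participants would be affected cannot be estimated from the documents. The ground for acting is participant safety and consistent site conduct. Nothing here says which renal rule is clinically right.

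**What to change.** Reconcile Sections 5.5, 7.4.4.4, 7.4.5.7 and 7.4.5.7.1 with Appendix 2.

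1. In Section 7.4.5.7.1, write out the full PRTD logic. Exchanging one connector is not enough: the text must say whether one lead criterion with two supporting findings qualifies, and whether the two lead criteria alone suffice.
2. In Section 5.5, complete the renal item and cross-refer to an explicit renal criterion.
3. State whether Section 7.4.4.4 or Section 7.4.5.7 governs a confirmed eGFR fall above 50%, or set out the order in which they apply, including the evidence needed before restart.

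Which thresholds and actions are kept is for the sponsor's clinicians. The cost is amended protocol wording and notice to sites; the laboratory data are already collected.

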7.4.5.8. Proteinuria

Participants with an abnormal urine microalbumin/creatinine ratio (>0.3 mg/mg, >300 mg/g, or >34 mg/mmol) that represents a change from Baseline and no associated increase in creatinine, should have a repeat spot urine microalbumin/creatinine ratio performed within 2-4 weeks. If confirmed, then consideration should be given to additional evaluation after consultation with the study medical monitor. Additional evaluation may include a 24-hour urine protein and creatinine measurement and nephrology referral.

Participants with an abnormal urine albumin/creatinine ratio (>0.3 mg/mg, 300 mg/g, or >34 mg/mmol and representing a change from Baseline) and a serum creatinine increase >45 μ mol/L (or 0.5 mg/dL) should have confirmation of both results within 2 weeks. If confirmed, the study medical monitor should be contacted immediately. Agreement on further management should be agreed between the investigator and medical monitor.

7.4.5.9. QTc Prolongation

Participants with an average QTc interval >550 msec from three or more tracings separated by at least 5 minutes should have IP discontinued. These criteria are based on an average QTc value of triplicate ECGs. If an ECG demonstrates a prolonged QT interval, obtain 2 more ECGs over a brief period (~5-10 minutes) and use the averaged QTc values of the 3 ECGs to determine whether the participant should be discontinued from the study. If an alternative cause of the QT prolongation is determined (e.g., participant receiving drug known to cause prolonged QT or TdP), then IP may be restarted after consultation with, and agreement by, the Medical Monitor.

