- For any participant who withdraws prematurely from the Maintenance or Extension Phase during a planned in-clinic study visit, withdrawal assessments and procedures are to be performed (according to the Time and Events Table (Section 7.1) instead of the assessments for the active planned visit during which the withdrawal decision is made.

Withdrawal decision occurs between planned clinic visits:

- In the event that a decision to withdraw a participant occurs between clinic visits, participants will be instructed to return for an unscheduled withdrawal visit (within 4 weeks of the last Q4W LA injection or within 8 weeks of the last Q8W LA injection received) during which withdrawal assessments according to the Time and Events Table (Section 7.1) will be completed. For participants who received one or more injections of CAB LA+ RPV LA **withdrawal assessments must occur prior to initiation of the next ART regimen.**

If withdrawal coincides with the active planned Week 52 or Week 100 visits, HIV-1 RNA will only be assessed if the last HIV-RNA measurement from Week 48 or Week 96 was ≥ 50 copies per mL (i.e. retest for viral load blip). This will ensure that only the Week 48 or Week 96 viral load assessments or required retest will be counted towards the primary and secondary efficacy endpoint windows.

The in-clinic visit will be recorded as an unscheduled withdrawal visit with the following exception. A withdrawal visit and assessments coinciding with the planned Week 100 visit will be recorded as the Week 100 visit such that the participant can be considered a completer, consistent with the definition of study completer in Section 5.6.

Participants may be prematurely discontinued from the study treatment for any of the following reasons:

- Adverse event / Serious adverse event
- Protocol deviation
- Intolerability of injections
- Participant lost to follow-up
- Participant or Investigator non-compliance;
- Termination of the study by the Sponsor
- At the request of the participant, Investigator, GSK or ViiV Healthcare;

- The participant requires concurrent prohibited medications during the course of the study. The participant may remain in the study if in the opinion of the Investigator and the medical monitor; such medication will not interfere with the conduct or interpretation of the study or compromise the safety of the participant.

Participants must be discontinued from study treatment for any of the following reasons:

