5.5.2. QTc Stopping Criteria

A participant who has a QTc interval >550 msec considered causally related to IP will be withdrawn from the study. The QTc should be based on averaged QTc values of triplicate electrocardiograms obtained over a brief (e.g., 5 to 10 minute) recording period.

If an alternative cause of the QT prolongation is determined (e.g., participant receiving drug known to cause prolonged QT or TdP), the IP may be restarted (or continued) after

consultation and agreement with the Medical Monitor. RPV and RPV LA should not be administered to patients who are receiving a drug known to be associated with TdP.

When performing ECGs, the *same* QT correction formula *must* be used for *each individual participant* to determine eligibility for, and discontinuation from, the study. This formula may not be changed or substituted once the participant has been enrolled.

For example, if a participant is eligible for the protocol based on QTcB, then QTcB must be used for discontinuation of this individual participant as well.

Once the QT correction formula has been chosen for a participant's eligibility, the *same formula* must continue to be used for that participant *for all QTc data being collected for data analysis*. Safety ECGs and other non-protocol specified ECGs are an exception.

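### For a QTc above 550 msec not considered related to study drug, Section 7.4.5.9 discontinues IP while Sections 5.5 and 5.5.2 do not require it

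*Protocol*

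**What the plan says.** **Section 5.5** opens its mandatory list with "Participants must be discontinued from study treatment for any of the following reasons". The QTc item reads "QT interval (QTc) interval >550 msec from three or more tracings separated by at least 5 minutes and considered causally related to IP".

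**Section 5.5.2** keeps the causality condition but names another action: "A participant who has a QTc interval >550 msec considered causally related to IP will be withdrawn from the study". It bases the QTc on averaged triplicate ECGs. Where an alternative cause of the prolongation is determined, "the IP may be restarted (or continued) after" consultation and agreement with the Medical Monitor.

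**Section 7.4.5.9** has no causality condition: "Participants with an average QTc interval >550 msec from three or more tracings separated by at least 5 minutes should have IP discontinued". After a prolonged reading, sites obtain two more ECGs and "use the averaged QTc values of the 3 ECGs to determine whether the participant should be discontinued from the study". Cause enters only afterwards. If an alternative one is determined, "then IP may be restarted after consultation with, and agreement by, the Medical Monitor"; continuing without a break is not offered.

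Three other places bear on the point:

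- **Section 7.4.10** sends the reader to 5.5.2 for QTc withdrawal criteria and does not mention 7.4.5.9.
- **Section 7.4.4.3** sets the general rule for Grade 3 events. With compelling evidence that IP is not the cause, dosing may continue after discussion with the Medical Monitor. If the event is related or possibly related, IP is withheld until the event has fallen to Grade 2 or lower.
- **Section 11.6.5** sets the causality standard. A reasonable possibility needs facts or arguments suggesting a causal link; being unable to exclude one is not enough.

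**The concern.** A site that opens the toxicity-management section and a site that opens the stopping criteria can treat the same confirmed ECG differently, each following the protocol. Scheduled ECGs are taken before dosing (Section 7.1, footnote h), so whether to inject can arise at the same visit.

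The consequences for the participant are large. Anyone who has had an injection and discontinues must start HAART and enters 52 weeks of long-term follow-up (Sections 4.2.4 and 6.10).

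For the analysis, the proportion discontinuing treatment because of adverse events is a secondary endpoint (Section 3). A participant stopped before the Week 48 window with no evaluable viral load counts as a non-responder on the key secondary endpoint (Section 9.3.2.1).

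**Working it through.** There is no stated figure to reproduce. The check sets the rules side by side for a confirmed average QTc above 550 msec.

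| Case | 5.5 | 5.5.2 | 7.4.5.9 |
|---|---|---|---|
| (a) Considered related to IP | Study treatment discontinued | Withdrawn from the study | IP discontinued |
| (b) Not considered related; alternative cause determined | Criterion not met | Criterion not met; IP may be restarted or continued if the Medical Monitor agrees | IP discontinued; may then be restarted if the Medical Monitor agrees |
| (c) Not considered related; no alternative cause determined | Criterion not met | Criterion not met | IP discontinued; no restart route given |

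**Case (a).** All three stop treatment. The only difference is the named action.

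**Case (b).** All three can end with the participant back on IP. They differ on whether dosing must stop first: a restart presupposes a stop, and only 5.5.2 offers continuation.

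**Case (c).** The rules conflict outright.

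**Can case (c) arise?** It would not if being considered related meant no more than finding no other cause. Two parts of the protocol speak against that reading. The 5.5 list uses both tests: the liver, renal and rash items turn on no compelling alternative cause being identified, while the QTc and Grade 4 items turn on a causal judgement. Section 11.6.5 then says that failure to rule out a link does not establish one. An unexplained prolongation can therefore properly be judged unrelated.

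**Does the Grade 3 rule settle it?** The grading table in Appendix 2 makes a QTc above 0.50 seconds at least Grade 3. Since 550 msec = 550/1000 = 0.55 seconds, and 0.55 > 0.50, Section 7.4.4.3 applies.

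- In case (b), a firm alternative cause may amount to compelling evidence. Dosing may then continue, which fits 5.5.2 and not 7.4.5.9.
- In case (c), compelling evidence will often be lacking, and an event thought possibly related is withheld. That is a temporary hold with a restart once the event is Grade 2 or lower. Section 7.4.5.9 gives no such route.
- An event judged neither possibly related nor compellingly unrelated is not covered by either bullet.

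The general rule narrows the disputed group and adds a fourth instruction for it.

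**Named actions.** Section 5.5 discontinues study treatment and 5.5.2 withdraws from the study. Section 7.4.5.9 discontinues IP in its first sentence and refers to discontinuation from the study later. These are not synonyms here: Section 5.5 separates leaving treatment from leaving the study, and Section 4.2.4 counts long-term follow-up as study participation.

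**The case against.** The best defence is that the sections can be read together. Section 7.4.5 calls itself general guidelines and 7.4.5.9 says should, whereas the 5.5 list says must and 7.4.10 points to 5.5.2. On that reading 5.5 and 5.5.2 decide withdrawal, and 7.4.5.9 describes a hold, an assessment of cause and a possible restart. Continuation under 5.5.2 still needs both a determined alternative cause and the Medical Monitor's agreement. Section 6.9 also requires decisions on interruption and resumption to be discussed with the Medical Monitor in advance.

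Part of this stands: case (b) becomes mostly a question of whether dosing pauses. It does not settle case (c). No passage gives 5.5.2 precedence over 7.4.5.9, and 7.4.5.9 itself says that the averaged value determines discontinuation from the study.

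A reader might infer four stronger points, which the documents do not support:

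- **Any such ECG stops treatment under one section only.** Not so: case (a) stops under all three.
- **Every disputed case meets a mandatory criterion.** The reverse holds. The cases are disputed because they do not meet the 5.5 criterion.
- **The timing of the tracings conflicts.** Tracings at 0, 5 and 10 minutes satisfy all three sections.
- **The primary endpoint is materially affected.** In Section 9.3.1, the route by which a discontinued participant without evaluable data counts as 50 c/mL or more because of the viral load at discontinuation is confined to reasons other than an adverse event.

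**Conclusion.** The contradiction is real but limited to a confirmed average QTc above 550 msec not considered causally related to IP. It is outright when no alternative cause is found, and concerns the interim stop when one is. The difference in named actions applies in every case.

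The protocol gives no event rate, so the number of cases cannot be estimated; they are presumed rare. On the key secondary endpoint, with 510 per arm, one participant moved from responder to non-responder changes that arm's crude proportion by 1/510 = 0.20 percentage points, against a margin of 10 points. The issue therefore concerns participant safety and consistent discontinuation data. It does not threaten the trial's inference.

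This rests on three assumptions: that the causality standard in Section 11.6.5 applies to the QTc items; that the QTc is read on a scale comparable with the grading table, which uses Bazett's formula while 5.5.2 lets the formula differ between participants; and that a QTc discontinuation is recorded as an adverse event.

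**What to change.** Reconcile Sections 5.5, 5.5.2 and 7.4.5.9 and state how they relate to 7.4.4.3, so that one answer is given to each of three questions:

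1. Is a causal judgement a condition of stopping, and what applies when the event is neither attributed to IP nor otherwise explained?
2. May dosing continue while cause is assessed?
3. Is the action interruption of IP, permanent discontinuation of study treatment, or withdrawal from the study?

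Section 7.4.10 should then point to the reconciled text. Which rule is adopted is a clinical decision for the sponsor, and none is proposed here. The cost is wording in one amendment and a note to sites, with no change to sample size or planned analyses.
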